12.1 Subsequent Anti-Cancer Therapies/Procedures

Subsequent anti-cancer treatment will be provided in a data listing with data retrieved from “Anti-Cancer Treatment after Discontinuation Details”, “Radiotherapy after Discontinuation Details”, and “Surgery after Discontinuation” eCRF pages. The earliest date of start of new anti-cancer *drug* therapy will be used for the definition of the on-treatment period; the earliest date of new anti-cancer therapy will be used for censoring for efficacy analyses.

Number and percentage of subjects with any subsequent anti-cancer treatment will be tabulated overall and by type of therapy based on the data collected from the “Anti-Cancer Treatment after Discontinuation” eCRF page.

Summary statistics will be created for best response across all post study treatments based on the data collected from “Systemic Anti-Cancer Treatment after Discontinuation Details” eCRF page.

13 Treatment Compliance and Exposure

The following analyses will be performed based on the SAF by dose level.

All dosing calculations and summaries will be based on the ‘Avelumab Administration’ eCRF page. A listing of study drug administration will be created with the information collected on the ‘Avelumab Administration’ eCRF page.

The derivations below are provided for the following:

- Avelumab administered as a 1-hour IV infusion at a dose of xx mg/kg once every 2 weeks in 2-week cycles

The dose level, denoted as “xx” will be determined from the dose escalation process. Analysis of exposure will be based on the calculated actual dose levels (total dose / weight).

13.1 Exposure to Study Drug

The dose level for avelumab is calculated as actual dose administered/weight (mg/kg). The last available weight of the subject on or prior to the day of dosing will be used.

The duration of avelumab treatment (in weeks) during the study for a subject is defined as:

$$\text{Treatment duration (weeks)} = (\text{last dose date} - \text{first dose date} + 14) / 7$$

The cumulative dose (mg/kg) of avelumab per subject in a time period is the sum of the actual dose levels that the subject received within that period (i.e., total dose administered (mg) / weight (kg)).

Each cycle for avelumab is defined by a 2-week period. The dose intensity (DI) and the relative dose intensity (RDI) will be calculated for each subject across all cycles. The dose intensity per cycle (mg/kg/cycle) is defined as

$$\text{DI (mg/kg/cycle)} = \text{Cumulative dose (mg/kg)} / [\text{duration of therapy (in weeks)} / 2]$$

The relative dose intensity (RDI) is defined as the actual dose intensity divided by the planned dose as specified in the protocol per cycle, denoted in the formula below as “xx”, and expressed in %. The dose level will be determined via the escalation process.

$$\text{RDI (\%)} = 100 \times [\text{DI (mg/kg/cycle)} / \text{xx (mg/kg)}]$$

The summary of treatment exposure and compliance for avelumab will include the following information:

- Treatment duration (weeks)
- Total number of infusions received
- Cumulative dose (mg/kg)
- Dose intensity (mg/kg/cycle)
- Relative dose intensity (%)

A listing of study treatment administration will be provided and will include subject identifier, age, study day, start date and time of the infusion as well as the kit number.

13.2 Partial Doses

According to the protocol, preplanned dose reductions are not allowed for avelumab. Any interruptions in delivering the planned dose that resulted in an actual non-zero dose less than the planned dose will be shown in the listing of study drug administration details.

13.3 Dose Delays

Dose delays (i.e. doses given greater than 14 days from the previous administration) will be shown on the listing of study drug administration details.

13.4 Infusion Rate Reductions

Infusion rate reductions as recorded on the eCRF will be identified as a dose modification in the listing of study drug administration details.

13.5 Infusion interruptions

Infusion interruptions, as recorded on the eCRF, will be shown on the listing of study drug administration details.

14 Efficacy Analyses

Analysis sets: FAS

14.1 Confirmed Best Overall Response per RECIST v1.1 (Secondary Endpoint)

Confirmed best overall response (BOR) will be assessed based on reported overall timepoint responses at different evaluation time points from the start date of study treatment until documented disease progression, according to the following rules according to RECIST 1.1:

- CR = at least two determinations of CR at least 4 weeks apart
- PR = at least two determinations of PR or better (PR followed by PR or PR followed by CR) at least 4 weeks apart (and not qualifying for a CR)
- SD (applicable only to subjects with measurable disease at baseline) = at least one SD assessment (or better) \geq 6 weeks after start date of study treatment (and not qualifying for CR or PR).
- Non-CR/non-PD (applicable only to subjects with non-measurable disease at baseline) = at least one non-CR/non-PD assessment (or better) \geq 6 weeks after date of randomization and before progression (and not qualifying for CR or PR).
- PD = progression \leq 12 weeks after start date of study treatment (and not qualifying for CR, PR, non-CR/non-PD or SD).
- Not Evaluable (NE): all other cases.

Only tumor assessments performed before the start of any further anti-cancer treatment will be considered in the assessment of BOR. Clinical deterioration will not be considered as documented disease progression.

Objective Response (OR) is defined as a confirmed BOR of CR or PR according to RECIST 1.1. Subjects who do not have an on-treatment radiographic tumor assessment due to early progression, who receive anti-tumor treatments other than the study treatments prior to reaching a CR or PR, or who die, progress, or drop out for any reason prior to reaching a CR or PR will be counted as non-responders in the assessment of OR. Each subject will have an objective response status (0: no OR; 1: OR).

The frequency (number) of subjects with BOR of CR, PR, SD, non-CR/non-PD (applicable only to subjects with non-measurable disease at baseline), PD, and NE will be tabulated. The confirmed Objective Response Rate by treatment group will be calculated along with the two-sided 95% CI

using the Clopper-Pearson method (exact CI for a binomial proportion as computed by default by the FREQ procedure using the EXACT option).

Subject's individual tumor assessments and BOR will be included in a listing. Additionally, for subjects with BOR of NE, the reason for having NE status will be included in the listing. The following reasons will be used:

- No post-baseline assessments due to death
- No post-baseline assessments due to other reasons
- All post-baseline assessments have overall response NE
- New anticancer therapy started before first post-baseline assessment
- SD of insufficient duration (<6 weeks after start date of study treatment without further evaluable tumor assessment)
- PD too late (>12 weeks after start date of study treatment)

Special and rare cases where BOR is NE due to both early SD and late PD will be classified as 'SD too early'.

14.2 Duration of Response per RECIST v1.1 (Secondary Endpoint)

Duration of Response (DOR) is defined, for subjects with a confirmed objective response, as the time from first documentation of objective response (CR or PR) to the date of first documentation of objective progression of disease (PD) or death due to any cause. If a subject has not had an event (PD or death), DOR is censored at the date of last adequate tumor assessment.

$$\text{DOR (months)} = [\text{date of event or censoring} - \text{first date of OR} + 1] / 30.4375$$

The censoring and event date options to be considered for the duration of response (DOR) analysis are presented in Table 2. DOR will be analyzed based on subjects in the FAS overall and by dose level with confirmed OR according to RECIST 1.1.

A swimlane plot indicating the time to and duration of response in months for each subject in the FAS will be provided. The plot will be color coded by dose level and will include symbols indicating the time of response (CR or PR) as well as time of progressive disease and end of treatment. If the subject has an ongoing response, this will be indicated.

A listing including subject ID, dose level, age, PD-L1 expression status, tumor type, the number of infusions, date of first objective response, date of event (PD or death), last tumor assessment date, duration of response (months), censoring status, and the event or censoring description will be provided.

In the absence of responders, these outputs will not be produced.

14.3 Time to Response per RECIST v1.1 (Secondary Endpoint)

Time to response (TTR) is defined, for subjects with an objective response, as the time from the start date of study treatment to the first documentation of objective response (CR or PR) which is subsequently confirmed.

TTR will be analyzed based on subjects in the FAS by dose level and overall with confirmed OR.

$$\text{TTR (in weeks)} = (\text{first date of OR} - \text{start date of study treatment} + 1) / 7$$

TTR will be summarized in the swimlane plot described in Section 14.2 and included in a subject data listing. In the absence of responders, these outputs will not be produced.

14.4 Progression Free Survival per RECIST v1.1 (Secondary Endpoint)

The PFS time, according to the RECIST 1.1, is defined as the time from the start date of study treatment until the first documentation of PD or death due to any cause, whichever occurs first. PFS data will be censored on the date of the last adequate tumor assessment for subjects who do not have an event (PD or death), for subjects who start a new anti-cancer therapy prior to an event or for subjects with an event after two or more missing tumor assessments. Subjects who do not have a baseline tumor assessment or who do not have any post-baseline tumor assessments will be censored on the start date of study treatment unless death occurred on or before the time of the second planned tumor assessment, in which case the death will be considered an event.

PFS time (in weeks) is defined as:

$$(\text{date of PD or death} - \text{date of the first dose of study treatment} + 1) / 7 \text{ (weeks)}.$$

Specific censoring rules are defined in Table 2.

Table 2 Outcome and event dates for PFS and DOR analyses

Scenario	Date of event/censoring	Outcome
No baseline assessment	Start date	Censored ^a
PD or death ≤ 12 weeks after last tumor assessment or ≤ 12 weeks after start date	Date of PD or death	Event
PD or death > 12 weeks after the last tumor assessment	Date of last adequate tumor assessment ^b documenting no PD before new anti-cancer therapy is given or missed assessments	Censored
No PD	Date of last adequate tumor assessment ^b documenting no PD before new anti-cancer therapy is given or missed assessments	Censored
Treatment discontinuation due to 'Disease progression' without documented progression	Not applicable	Information is ignored. Outcome is derived based on documented progression only.
New anti-cancer therapy given	Date of last adequate tumor assessment ^b documenting no PD before new anti-cancer therapy is given or missed assessments	Censored

^a However if the subject dies ≤12 weeks after start date the death is an event with date on death date

^b If there are no adequate post-baseline assessments prior to the PD or death, then the time without adequate assessment should be measured from the date of first dose of study treatment; if the criteria were met the censoring will be on the date of first dose of study treatment

Censoring reasons will be listed according to the categories in Table 3 following the hierarchy shown.

Table 3 PFS censoring reasons and hierarchy

Hierarchy	Condition	Censoring Reason
1	No baseline assessment	No baseline assessment
2	Start of new anti-cancer therapy before event.	Start of new anti-cancer therapy
3	Event more than 12 weeks after last adequate post-baseline tumor assessment	Event after missing assessments ^a
4	No event and [withdrawal of consent date ≥ date of first dose of study treatment OR End of study (EOS) = Subject refused further FU]	Withdrawal of consent
5	No event and lost to follow-up in any disposition page	Lost to follow-up
6	No event and [EOS present OR disposition page for any EPOCH after screening says patient will not continue into any subsequent phase of the study] and no adequate post-baseline tumor assessment	No adequate post-baseline tumor assessment
7	No event and none of the conditions in the prior hierarchy are met	Ongoing without an event

^a more than 12 weeks after last adequate tumor assessment.

Kaplan-Meier estimates (product-limit estimates) will be presented with a summary of associated statistics including the median survival time with two-sided 95% CIs. In particular, the

progression-free survival rate at 4, 8, 12, and 24 weeks will be estimated with corresponding two-sided 95% CIs. The CIs for the median will be calculated according to Brookmeyer and Crowley (4) and the CIs for the survival function estimates at the time points defined above will be derived using the log-log transformation according to Kalbfleisch and Prentice (5) (confype=loglog default option in SAS Proc LIFETEST) with back transformation to a CI on the untransformed scale. The estimate of the standard error will be computed using Greenwood's formula.

Frequency (number and percentage) of subjects with an event (progressive disease or death) will be presented.

A listing including subject ID, dose level, age, first and last dosing date, date of event (PD or death), the PFS time or censoring time, and the reasons for censoring will be provided.

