- y. Tumor assessments post-Baseline: Tumor evaluation has a time window of 5 days prior to dosing (-5 days) and  $\pm 5$  days after the EOT Visit. CT or MRI scans will be performed every 4 treatment cycles (every 8 weeks) for the first 24 weeks, then every 12 weeks thereafter. If bone metastases were present at Baseline, or if new bone metastases are suspected, bone scintigraphy or  $^{18}\text{F}$ FDG-PET/CT will be repeated every 8 weeks for the first 24 weeks, then every 12 weeks thereafter. Bone imaging is also required at the time of CR confirmation for subjects who had bone metastases at Baseline. If PR, CR, or PD is observed according to RECIST 1.1, a confirmation CT or MRI should be performed, preferably at the regularly scheduled 8-week assessment but no sooner than 4 weeks after the first documentation of response or confirmed disease progression. Tumor assessment should be repeated at the EOT Visit if more than 4 weeks have passed since the last evaluation.
- z. Registration prior to dosing: Registration of subjects will proceed through the use of an interactive response technology system.
- aa. Pretreatment: Premedication with an antihistamine (H1 receptor blocker such as diphenhydramine) and with paracetamol (acetaminophen) approximately 30 to 60 minutes prior to the first 4 doses of avelumab is mandatory. Premedication can be administered for subsequent avelumab doses based upon clinical judgment and presence/severity of prior infusion reaction. This regimen may be modified based on local treatment standards and guidelines as appropriate provided it does not include systemic corticosteroids.
- bb. Avelumab administration: Avelumab will be given as a 1-hour infusion every 2 weeks (14 days). The biweekly, 14-day treatment schedule should be strictly adhered to, returning to the target date even if the previous visit was off schedule.

**Table 2** Schedule of Assessments – Pharmacokinetic and Antidrug Antibody Sampling

	Treatment Period (-3/+1 days) 1 Cycle = 14 Days									Follow-up Visits	
	Cycle 1 (Week 1)	Cycle 2 (Week 3)	Cycle 3 (Week 5)	Cycle 5 (Week 9)	Cycle 7 (Week 13)	Cycle 8 (Week 15)	Cycle 13 (Week 25)	Cycle 19 (Week 37)	Cycle 25 (Week 49) and Every 6 Cycles Thereafter	EOT/ Withdrawal Visit (Within 7 Days of Decision to Discontinue)	30-Day Safety Follow- up (± 5 Days)

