### 7.3 Efficacy Assessments

To determine the ORR, the anticancer activity of avelumab will be evaluated by performing CT/MRI scans until confirmed disease progression or the start of new anticancer therapy.

A CT or MRI will be performed every 8 weeks for the first 24 weeks, then every 12 weeks thereafter (a window of 5 days prior to dosing is allowed, and  $\pm 5$  days at the End of Treatment Visit). In case partial response (PR), complete response (CR), or progressive disease (PD) is observed according to RECIST 1.1, a confirmation CT or MRI should be performed according to RECIST 1.1, preferably at the regularly scheduled 8-week assessment interval, but no sooner than 4 weeks after the initial documentation of response or confirmed disease progression. Tumor assessment should be repeated at the End of Treatment Visit if more than 4 weeks have passed since the last evaluation.

Treatment decisions will be made by the Investigator based on the Investigator's assessment of disease status. Investigator's assessment of objective tumor response to treatment will be performed according to RECIST 1.1 (all measurements should be recorded in metric notation, as described in RECIST 1.1).

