#### Phase II

- DOR, TTR, PFS per RECIST 1.1 and as adjudicated by the Investigator, and OS
- Occurrence and severity of TEAEs, AEs of special interest, and treatment-related AEs, and incidence of laboratory abnormalities, as graded by NCI-CTCAE v4.03
- Vital signs (including blood pressure and heart rate)
- Single- and multiple-dose PK profiles of avelumab (ie,  $C_{max}$ , AUC,  $t_{1/2}$ , and  $C_{trough}$ , as data permit)
- Immunogenicity as measured by avelumab ADA, including NABs

- Assessment of tumor PD-L1 expression; tumor-infiltrating T-cell activity; T-cell population; and T-cell, B-cell, and NK-cell numbers at Baseline and at confirmed progression (if tumor tissue is obtained)
- Vaccination-related antibody concentrations.

**Duration of response** is defined, for subjects with an OR, as the time from first documentation of OR (CR or PR) to the date of first documentation of objective PD or death due to any cause, whichever occurs first. If a subject has not had an event (PD or death), DOR is censored at the date of last adequate tumor assessment. Censoring rules are the same as for PFS.

**Time to response** is defined, for subjects with an OR, as the time from the date of first dose of avelumab to the first documentation of OR (CR or PR), which is subsequently confirmed.

**Progression-free survival** is defined as the time from the date of first dose of avelumab to the date of the first documentation of objective PD per RECIST 1.1 or death due to any cause, whichever occurs first. Progression-free survival data will be censored on the date of the last adequate tumor assessment for subjects who do not have an event (PD or death), for subjects who start a new anticancer therapy prior to an event, or for subjects with an event after 2 or more missing tumor assessments. Subjects who do not have a Baseline tumor assessment or who do not have any post-Baseline tumor assessments will be censored on the start date unless death occurred on or before the time of the second planned tumor assessment, in which case the death will be considered an event.

**Overall survival** is defined as the time from the date of first dose of avelumab to the date of death due to any cause. Subjects last known to be alive will be censored at date of last contact.

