#### 8.5.3.2 Phase I and Phase II: Other Efficacy Endpoints

The following parameters will be calculated using the FAS:

- DOR in subjects with confirmed BOR of CR or PR: time (in months) from the first occurrence of CR or PR to either PD or occurrence of death due to any cause
- TTR, which is the time (in months) from the date of first dose of avelumab to the first documentation of OR (CR or PR), which is subsequently confirmed
- PFS, which is the time (in months) from first study drug administration to either first observation of PD or occurrence of death due to any cause within 12 weeks of the last tumor assessment, whichever occurs first
- OS time (in months), calculated for all subjects.

Duration of response, PFS, and OS will be presented in subject listings and analyzed using the Kaplan-Meier method in FAS by dose/cohort. Time to response will be presented in subject listings

and summarized including number of subjects (n); mean, standard deviation; median, Q1, Q3, minimum, and maximum by dose/cohort.

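### SAP Table 2 censors PFS events after a 12-week gap, but two scan intervals in this trial span 16, 20 or 24 weeks, so the table does not apply the two-missed-assessments rule stated above it

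*SAP*

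**What the plan says.** The documents contain three versions of the rule.

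- **Two missed assessments.** The SAP 14.4 text censors PFS for "subjects with an event after two or more missing tumor assessments". Protocol 8.3.2 says the same: "for subjects with an event after 2 or more missing tumor assessments".
- **A 12-week gap for progression or death.** SAP 14.4 then refers to Table 2 for the specific rules, and Table 2 censors "PD or death > 12 weeks after the last tumor assessment". Table 3 row 3 repeats the limit ("Event more than 12 weeks after last adequate post-baseline tumor assessment") and gives as the censoring reason that the event came after missing assessments. So 12 weeks is meant to represent missed scans.
- **A 12-week gap for death only.** Protocol 8.5.3.2 counts "occurrence of death due to any cause within 12 weeks of the last tumor assessment" and attaches no such limit to progression.

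For subjects with no baseline or no post-baseline scan, the SAP text censors at first dose "unless death occurred on or before the time of the second planned tumor assessment". Table 2 row 2 and footnotes a and b use 12 weeks from the start date instead.

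Protocol 7.3 sets the schedule: "A CT or MRI will be performed every 8 weeks for the first 24 weeks, then every 12 weeks thereafter". SAP Section 7 declares accordance with protocol version 2.0 and lists changes to analysis sets only.

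**The concern.** A fixed 12-week limit equals two scan intervals only if scans are 6 weeks apart, and this trial has no 6-week interval. The table is therefore stricter than the text at every point in the schedule, and the same subject can be an event under one rule and censored under the other. A documented progression can drop out of the event count, and in one case it contributes no follow-up time at all.

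This affects the PFS event counts, the Kaplan-Meier median and the planned landmark rates (4, 8, 12 and 24 weeks). It also affects the censoring reasons, which would report missed assessments for subjects who missed one scan or none. Duration of response uses the same table, but it appears only in a listing and a swimlane plot, and only if there are responders.

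**Working it through.** **Inputs.** First on-study scan at Cycle 5, Day 57 (protocol 7.1.2). Scans every 8 weeks to Week 24, then every 12 weeks (protocol 7.3), so planned days are 57, 113, 169, 253, 337. Scans may be up to 5 days early (protocol Table 1, footnote y), and the visit itself may move by -3/+1 days (Table 1, treatment-period footnote). The Table 2 limit is 12 × 7 = 84 days.

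**The plan's figure.** 84 days is 2 × 42 days. Two intervals here are 8 + 8 = 16, 8 + 12 = 20 or 12 + 12 = 24 weeks, so the 12-week limit cannot be derived from the schedule.

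**1. One missed scan, progression at the next planned scan.**

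| Last scan | Missed | Progression found | Gap (days) | Table 2 | Text |
|---|---|---|---|---|---|
| none (first dose, Day 1) | Week 8 | Day 113 | 113 - 1 = 112 | censored at Day 1 (footnote b) | event |
| Day 57 | Week 16 | Day 169 | 169 - 57 = 112 | censored at Day 57 | event |
| Day 113 | Week 24 | Day 253 | 253 - 113 = 140 | censored at Day 113 | event |
| Day 169 | Week 36 | Day 337 | 337 - 169 = 168 | censored at Day 169 | event |

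The shortest such gap the windows allow is (169 - 3 - 5) - (57 + 1) = 103 days, still above 84. Only an End of Treatment or unscheduled scan in between could bring the gap to 84 days or less.

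**2. No missed scan, after Week 24.** The nominal gap, 253 - 169 = 84 days, is an event. It exceeds 84 whenever the earlier scan is further ahead of its nominal day than the later one. If both scans follow the same distribution of offsets, the share of gaps above 84 days is (1 - P(same offset)) / 2.

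- All scans on the nominal day: 0%.
- 90% on the day, the rest even over -5 to -1: P(same) = 0.81 + 0.01/5 = 0.812, giving 9.4%.
- 50% on the day: P(same) = 0.25 + 0.25/5 = 0.30, giving 35%.
- Even over -5 to 0: P(same) = 1/6, giving 15/36 = 42%, with a maximum gap of 84 + 5 = 89 days.
- Visit window also used evenly: (900 - 110)/2 = 395 of 900 pairs, 44%, with a maximum of 84 + 5 + 4 = 93 days.

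The resulting censoring falls no earlier than Day 169 - 5 = 164, so this part barely touches the planned landmarks.

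**3. Death without a post-baseline scan.** The text counts deaths to the second planned assessment, Week 16 (Day 113). Table 2 stops at start + 84 days (Day 85). Deaths on Days 86 to 113, a span of 28 days, are events in the text and censored at Day 1 in the table. Footnote a does the same for subjects with no baseline scan.

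**4. Size, by simulation.** The documents give no progression or missed-scan rates, so these are assumptions: exponential PFS with median 8, 16 or 26 weeks; scans on nominal days; each missed independently; no deaths and no End of Treatment or unscheduled scans; 400,000 subjects per setting.

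| Scans missed | Progressions censored, Table 2 | Progressions censored, text |
|---|---|---|
| 5% | 7-9% | 0.4-0.6% |
| 10% | 14-17% | 1.7-2.3% |
| 20% | 28-33% | 6-9% |

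At 10% missed, Week 12 PFS is 51% (Table 2) against 54% (text) for a median of 8 weeks. Week 24 PFS is 69% against 67% for a median of 26 weeks. The direction is not fixed. Weeks 4 and 8 do not change, because the first scan falls at 57/7 = 8.14 weeks by the SAP formula; an effect there would need early deaths or unscheduled progression.

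**The case against.** Several points on the other side are fair.

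- **Table 2 is named as governing, and Table 3 agrees with it.** A programmer would probably follow the tables. But the SAP then departs from protocol 8.3.2 and from its own text, and Section 7 does not say so.
- **The 12 weeks has a source in protocol 8.5.3.2.** That covers deaths after a scan. It does not cover progression, and it conflicts with protocol 8.3.2, so it is a further version to reconcile.
- **The text rule is not uniformly more accurate.** With no scans missed, Week 12 PFS at a median of 8 weeks is 50%; Table 2 gives 51% and the text 54%. Across all nine simulated settings Table 2 is closer to the full-scan value at Week 12, while the text rule is closer or tied at Week 24. This stands, so the fault lies in the unresolved contradiction and the limit unrelated to the schedule, not in a bias of known sign.
- **The effect is small beside the sampling error.** Phase I plans 12 to 36 subjects. The standard error of a 50% rate is √(0.25/36) = 8 points at best and √(0.25/12) = 14 at worst. In simulated trials of 12 subjects with 10% missed, the two rules gave the same estimate in 42% (Week 12, median 8) to 56% (Week 24, median 26). This also stands.
- **End of Treatment scans would close some gaps.** They are due if more than 4 weeks have passed since the last evaluation, so the simulated censoring shares are probably too high. The schedule arithmetic does not depend on them.

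**Conclusion.** The concern holds: Table 2 and Table 3 row 3 do not implement the rule that SAP 14.4 and protocol 8.3.2 state. Three results need no assumption about rates. With no intervening scan, a single missed planned scan is enough to censor progression found at the next one. After Week 24, in-window timing can censor progression with no scan missed. There is a 28-day span in which early deaths are classified differently.

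How often this would matter depends on the assumed progression and missed-scan rates. In the settings tried, Table 2 censored several times as many progressions as the text rule, and the landmark differences quoted above were 2 to 3 points, in either direction. PFS is secondary, with no hypothesis test, so no sample size or dose decision is affected. It should be fixed because two rules in one section leave it open which events count, and in a trial this small one or two reclassified subjects move the reported figures.

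**What to change.** In SAP Table 2 (rows 2 and 3, footnotes a and b) and Table 3 row 3 with its footnote, replace the 12-week limit with a count of planned assessments (Weeks 8, 16, 24, 36, 48 and so on). Censor only if two or more consecutive planned assessments were missed between the last adequate assessment (scheduled, unscheduled or End of Treatment) and the event. State when a planned scan counts as missed: the documents give 5 days early, the -3/+1 visit window and ±5 days at End of Treatment, and any further allowance for lateness must be defined. For subjects with no baseline or no post-baseline scan, count deaths up to the second planned assessment (Week 16, Day 113, with its window). Record in SAP Section 7 that this follows protocol 8.3.2 and replaces the 12-week wording of protocol 8.5.3.2.

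If the sponsor does intend 12 weeks, the SAP text must change to match, and Section 7 must list the departure with a reason and an allowance for scan windows.

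The cost is wording in two tables and Section 7, plus a small programming change to count missed planned scans. No new data are needed. PFS estimates may move in either direction.
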